3.2. Effectiveness analyses

3.2.1. Effectiveness analyses

Primary outcome

Relative risk of death in-hospital (within 30d) in the intervention arm vs death in-hospital (within 30d) in the standard of care arm, estimated by univariable generalised estimating equation under a binomial model with a log link and assuming an exchangeable correlation structure. Clustering will be assumed to be on hospitals within countries in a fully nested framework.

Secondary outcome

Relative risk of death in-hospital or severe complication (within 30d) in the intervention arm vs death in-hospital or severe complication (within 30d) in the standard of care arm. Analysis approach will be as in primary outcome.

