3.2.2. Sensitivity and subgroup analyses on the effectiveness outcomes

Sensitivity analysis will investigate the potential for unobserved outcomes (transfer out or lost to follow up) to impact primary and secondary effectiveness estimates. Under the same model as the primary (secondary) effectiveness outcomes individuals with unobserved outcomes (lost to follow up) will alternately be assumed to be alive at discharge (censored at thirty days) or to have died in-hospital within 30 days. These estimates and confidence intervals will be plotted along with the primary (secondary) effectiveness estimates.

Primary and secondary endpoints will be analysed under the same model as the primary analysis for the following subgroups treated as stratification variables:

- i) hospital level (primary, secondary, tertiary),
- ii) duration of recruitment (1, 2, 3 or 4 weeks)
- iii) Calendar time (quarters)
- iv) Income category of country (low or middle, according to the World Bank classification in 2020)

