3.2.3. Patient risk factors and patient level analysis

A prespecified patient level analysis will be undertaken including all high-risk individuals with data in a standard of care hospital, and all high-risk individuals in an intervention arm who can be presumed to be exposed to the intervention (definition 1: poster and one other intervention on day 0 and day 1; definition 2: any 2 interventions on day 0 and day 1). The relative risk of experiencing the primary (secondary) outcome by exposure to intervention (as defined above) will be estimated in stratified models for the following individual characteristics:

- I. age (years)
- II. ASA status (1-5)
- III. surgical procedure category (Gynaecologic, Obstetric, Neuro, ENT, Orthopaedic, Plastics and Breast, Urology, Gastrointestinal and Hepatobiliary, Cardiothoracics, Other)
- IV. indication for surgery (non-communicable disease, caesarean section, trauma, infection)
- V. urgency of surgery (elective, urgent, emergent)
- VI. severity of surgery (minor, intermediate, major)

This concludes the pre-specified analyses for ASOS-2. Further exploration of the data will take place.

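### SAP 3.2.2 estimates effects by subgroup but specifies no treatment-by-subgroup test and no rule for reading the results, so it cannot show whether the effect differs between subgroups

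*Combined protocol and SAP*

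**What the plan says.** SAP section 3.2.1 gives the primary model: a relative risk "estimated by univariable generalised estimating equation under a binomial model with a log link and assuming an exchangeable correlation structure". Univariable means that arm is the only covariate.

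SAP section 3.2.2 then applies that same model to both endpoints "for the following subgroups treated as stratification variables". The four factors are "hospital level (primary, secondary, tertiary"), "duration of recruitment (1, 2, 3 or 4 weeks"), "Calendar time (quarters") and "Income category of country (low or middle, according to the World Bank classification in 2020").

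SAP section 3.2.3 takes a similar route for six patient characteristics. Among high-risk patients, with the intervention arm restricted to those presumed exposed, the relative risk "will be estimated in stratified models for the following individual characteristics". The SAP then closes the list of pre-specified analyses.

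The only inference rule is in protocol section 7.2: two-sided p below 0.05, written for the effect on the primary and secondary outcomes. The contents list names a protocol section on subgroup analyses with a broken bookmark, and the body has no such section.

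**The concern.** Whether an effect differs between subgroups is a question about the contrast between strata. A model whose only term is arm, run by stratum, gives one relative risk per stratum and no measure of that contrast. A reader is left to compare strata by eye, usually by asking which confidence intervals exclude 1. The trial was sized for 80% power in the whole sample, so each stratum is underpowered and significance will vary between strata by chance even if the intervention works equally well everywhere.

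Hospital level and country income are the kind of factor on which a reader might judge where the intervention works. The documents tie no roll-out decision to these results. What is at stake is the interpretation of secondary tables, not the trial's main conclusion.

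**Working it through.** **Inputs.** From protocol section 7.1 and Table 1: control 2.0%, intervention 1.5% (relative risk 0.75), ICC 0.015, CV 0.63, mean cluster size 100, 80% power, two-sided alpha 0.05, 664 clusters. Allocation is taken as 1:1 (protocol section 6.3: block size 2, control share held at 48–52%).

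**Assumptions.** Stratum sizes are not in the documents, so equal strata are assumed first and unequal shares are then tried. The number of quarters is not stated; recruitment from May 2019 to March 2020 touches four. That gives 3 + 4 + 4 + 2 = 13 strata.

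**1. The plan's own figure**
- n per arm without clustering = [1.96√(2 × 0.0175 × 0.9825) + 0.8416√(0.02 × 0.98 + 0.015 × 0.985)]² / 0.005² = 10,795.
- Design effect = 1 + ((1 + 0.63²) × 100 − 1) × 0.015 = 3.080.
- Clusters = 2 × 10,795 × 3.080 / 100 = 665, against 664 stated. The other two rows of Table 1 also reproduce (536.5 against 536; 1068.3 against 1068).
- At 664 clusters the effective size per arm is 33,200 / 3.080 = 10,778, and power is 79.9%.

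**2. Power per stratum under a uniform relative risk of 0.75**

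For k equal strata, n_k = 10,778 / k, and power q = Φ{[0.005√n_k − 1.96 × 0.1854] / 0.1854}. The chance that some strata of a factor are significant and others are not is 1 − q^k − (1 − q)^k.

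| Factor | k | n_k per arm | q | Strata disagree |
|---|---|---|---|---|
| Income | 2 | 5,389 | 51% | 50% |
| Hospital level | 3 | 3,593 | 37% | 70% |
| Duration; quarter | 4 | 2,694 | 29% | 74% |

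With unequal shares (30/70 for income, 10/30/60 for level, 10/15/25/50 for duration, 10/20/30/40 for quarter) the chance of disagreement is 55%, 74%, 75% and 74%.

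**3. No effect anywhere**

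In a simulation with the four factors fully crossed (40,000 runs):
- At least one of the 13 strata reaches two-sided p<0.05 in about 42% of trials, for one outcome. Equal and unequal shares give the same figure to within a percentage point.
- Counting only strata significant in the direction of benefit, the figure is about 21–22%.
- At least one of four interaction tests at 0.05 rejects in about 18% (by formula, 1 − 0.95⁴ = 18.5%). With Holm correction over the four factors this is about 5%.

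The 42% and the 18% concern different hypotheses (an effect in some stratum; a difference between strata), so the gap between them does not measure what the fix gains.

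**4. Power of the interaction test**

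The whole-trial SE of the log relative risk is √[0.98 / (10,778 × 0.02) + 0.985 / (10,778 × 0.015)] = 0.103. With two equal strata, the SE of the difference in log relative risks is 2 × 0.103 = 0.206. Power for a ratio of relative risks of 0.75 is Φ(0.288 / 0.206 − 1.96) = 29%; for 0.60 it is 70%.

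**5. Section 3.2.3**

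The five categorical characteristics have 5 + 10 + 4 + 3 + 3 = 25 levels. Over two exposure definitions and two outcomes, that is 100 stratum estimates. Age is listed in years, with no strata defined.

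**The case against.** The strongest reply is that sections 3.2.2 and 3.2.3 plan estimation only. Neither mentions stratum p-values, comparing significance between strata, or claiming effect modification. A reader might infer that chance differences are likely to be reported as real; the documents do not say so, and that reading is not supported. What stands is that the plan gives neither a test nor a rule to prevent it.

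The stratification wording in 3.2.2 could also mean a pooled analysis adjusted for strata. Separate estimates are the more natural reading, since the factors are called subgroups and the model is univariable. On either reading no interaction is tested.

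The figures have limits. The mixed picture is a consequence of low stratum power, and it remains in the table after the fix; only its interpretation is protected. The 42% counts apparent harm as well as benefit. Mean size 100 and CV 0.63 are applied in every stratum, which is rough for duration of recruitment: under protocol section 7.1 sites stop early because they have passed 100 patients, while sites below 100 stop at four weeks.

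Finally, an interaction test would have low power. That is a reason to call the subgroups exploratory, not to leave out the one test that addresses the question.

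**Conclusion.** The point holds as a gap in the subgroup plan. As written, section 3.2.2 cannot show whether the effect differs by hospital level, duration, quarter or income. If the effect is uniform at 0.75, the strata of a factor would disagree on significance in about half to three quarters of trials. This rests on Table 1's inputs, on assumed stratum shares and, for the quarter factor, on four quarters.

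Two stronger inferences should be avoided. The main analyses of the primary and secondary outcomes in section 3.2.1 are not put in doubt. Nor can the remedy for 3.2.2 be copied into 3.2.3: there the intervention arm is selected on exposure, so an interaction test would compare contrasts that are no longer randomised. This is worth correcting, but it concerns secondary reporting.

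**What to change.** **Section 3.2.2.** Replace the stratification wording with the following:
- For each factor with k levels, fit the primary GEE in all patients with arm, subgroup (k − 1 terms) and arm-by-subgroup (k − 1 terms).
- Report stratum relative risks with 95% confidence intervals beside one interaction p-value per factor and outcome.
- Claim a subgroup difference only on the interaction test.
- State the number of tests (four factors × two outcomes = eight) and label the subgroups exploratory. Holm correction is optional; if used, say whether it spans both outcomes.

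**Section 3.2.3.** Label the stratified estimates exploratory and non-randomised, state that they will not be used to claim effect modification, and define the age strata.

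**Cost.** SAP wording and 2(k − 1) extra terms per model: two for income, four for hospital level, six each for duration and for four quarters. A log-link binomial GEE with an outcome near 2% may fail to converge in sparse strata, so name a fallback. Few subgroup claims will be possible, given interaction power of about 29% for a ratio of relative risks of 0.75 with two equal strata. No new data are needed.

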5.2 Inclusion criteria

[figure not shown]
- Patients
 - All consecutive adult patients aged 18 years and over admitted to participating centres undergoing elective and non-elective surgery
- Participating surgical centres
 - Randomised according to a stratification based upon the level of the surgical facility and the surgical case load. Recruitment will run until March 2020.

We plan to randomise 664 hospitals to either increased postoperative surveillance or standard care for high-risk adult (≥ 18 years) surgical patients. The follow up is in-hospital. This study will be registered on ClinicalTrials.gov.

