6.3. Randomisation

Participating sites will be randomised to normal postoperative care (“SOC”), or increased postoperative surveillance (“Intervention”) in four recruitment blocks (calendar time blocks). Randomisation in each block will be stratified by country and by level of the surgical facility with a fixed block size of 2. The randomisation algorithm will seek to balance randomisation arms by simulating randomisations with an automated filter to screen out poorly balanced randomisations. In the second and subsequent recruitment blocks, the randomisation algorithm will use knowledge of the previous randomisations and a similar simulation and filtering approach to ensure reasonable balance across arms and across level of surgical facility. This approach was developed on the basis of a simulation model for the randomisation that was used to evaluate the probability of overall balance of randomisation arms and balance within level of care strata if randomising recruitment phases in waves. Results of 10,000 simulation runs indicated that a balanced simulation within the bounds described below would be obtained >50% of the time without the filtering step.

The algorithm is described briefly here:

For recruitment phase 1:

1. Simulate stratified block randomisation within country and level of facility
2. Check that simulated randomisation has percent SOC between [48% - 52%]
3. If NO, then repeat steps 1 and 2. If YES then use this randomisation.

For all other recruitment phases:

1. Simulate stratified block randomisation for this phase within country and level of facility
2. Combine this simulation with prior actual randomisations
3. Check that combined randomisation has percent SOC between [48% - 52%]
4. If NO, then repeat steps 1-3. If YES proceed to next check.
5. Check that combined randomisation has balance within level of care between [45% - 55%]
6. If NO, then repeat steps 1-5. If YES then use this randomisation.

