7.1. Sample size calculation

This is a cluster randomised trial of hospitals in Africa. We will match hospitals on expected surgical volume in a week of surgery. This varied tremendously across the ASOS group; with a median number of surgical procedures per hospital for the study week in ASOS of 29 (IQR 10-71).⁸ The variability of the individual patient outcomes explained by the cluster (or surgical site) is taken into account in these sample size calculations. The intra-cluster correlation coefficient (ICC) in ASOS was 0.01. For the sample size calculation, we have therefore used a conservative ICC of 0.015.

Based on ASOS, we estimate the coefficient of variance for a 4-week recruitment period to be 0.63. A 4-week recruitment period is defined as the following; i) hospitals stop recruiting at the end of the week in which they have exceeded 100 enrolled patients, and ii) if a site had not reached 100 enrolled patients after 4 weeks of recruiting, it would stop recruiting.

The incidence of mortality in ASOS was 2.1%.⁸ We expect a 25% relative risk reduction in mortality through increased surveillance of postoperative surgical patients at high-risk of severe complications or in-hospital mortality. Based on the intra-cluster correlation coefficient (ICC) for the composite of severe complications and mortality in ASOS-2 of 1.5%, a coefficient of variance of 0.63, and stratification for the level of the surgical facility, and the volume of procedures per week, a trial for efficacy of increased postoperative surveillance would require 64,200 patients, from 642 surgical centres across Africa (Table 1).⁸ Based on a relative risk reduction of 25% in the intervention arm, the sample sizes for the primary outcome are shown in Table 1.

TABLE 1: Sample size calculations for the ASOS-2 Trial based on a power of 80%, 2-sided $\alpha = 0.05$ and a mean cluster size of 100 patients

Primary outcome (in-hospital all-cause mortality)					
Control event rate	Intervention arm	Relative risk	Intra-cluster correlation coefficient (ICC)	Coefficient of variance (CV)	Total clusters
2.0%	1.5%	0.75	0.015	0	536
2.0%	1.5%	0.75	0.015	0.63	664
2.0%	1.6%	0.80	0.015	0.63	1068

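### The recruitment-duration subgroup is formed by enrolment after allocation, so comparisons of the arms within it are not protected by randomisation

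*Combined protocol and SAP*

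**What the plan says.** SAP 3.2.2 lists four subgroups. The second is "duration of recruitment (1, 2, 3 or 4 weeks". The instruction for all four is: "Primary and secondary endpoints will be analysed under the same model as the primary analysis for the following subgroups treated as stratification variables". This yields an intervention-versus-control estimate for each number of weeks, for both endpoints.

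Protocol 7.1 defines what fixes the number of weeks: "hospitals stop recruiting at the end of the week in which they have exceeded 100 enrolled patients", and "if a site had not reached 100 enrolled patients after 4 weeks of recruiting, it would stop recruiting". Duration is thus a record of enrolment speed, capped at four weeks.

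Duration is not a randomisation factor. Protocol 6.3 states: "Randomisation in each block will be stratified by country and by level of the surgical facility with a fixed block size of 2". SAP 3.1 names hospital level only. Two other places mention hospital volume: 5.2 describes stratification on "the level of the surgical facility and the surgical case load", and 7.1 says "We will match hospitals on expected surgical volume in a week of surgery". The centre data listed in 6.5 include beds and operating rooms but no surgical volume.

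No masking is described. Under 6.4 and Appendix 3, intervention sites score risk, provide surveillance, post a bedside guide and complete a case record form specific to their arm.

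**The concern.** A subgroup comparison keeps the benefit of randomisation only if the subgroup is defined by something the allocation cannot influence. Duration of recruitment can be influenced. Staff know their arm when they enrol, and the intervention form adds a day-by-day surveillance grid for high-risk patients. If that slows capture of eligible patients, a hospital of a given size can fall into a longer-duration level because of its arm.

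Each level would then hold larger hospitals in one arm than in the other. If mortality is related to hospital volume, the comparison within the level mixes hospital size with treatment. The displacement has the same sign at every level, so four stratum estimates could appear to agree on a benefit or a harm that is not there.

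**Working it through.** **The plan's own figure.** The plan gives no figure for this subgroup. Table 1 was reproduced to confirm the reading of the design inputs (2.0% v 1.5%, ICC 0.015, CV 0.63, mean cluster size 100):
- n per arm = 7.849 × (0.02×0.98 + 0.015×0.985) / 0.005² ≈ 10,792
- design effect = 1 + ((1 + 0.63²)×100 − 1)×0.015 = 3.0803
- clusters = 2 × 10,792 × 3.0803 / 100 ≈ 665, against 664 stated.

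**Inputs for the check.** From the documents: weekly volume median 29, IQR 10-71, and the stopping rule (both 7.1). Assumed: log-normal volume; intervention sites enrol a fraction f of eligible patients while control sites enrol all; missed patients have average risk; hospital mortality is multiplied by s per doubling of volume; the true relative risk is 1.

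**Step 1: how the levels move.** Ignoring week-to-week variation, a control site with weekly volume v finishes in week 1 if v > 100, week 2 if 50 < v ≤ 100 and week 3 if 33.3 < v ≤ 50; otherwise it runs four weeks. With f = 0.8 each cut-point is divided by 0.8, giving 125, 62.5 and 41.7. A hospital with 110 cases a week finishes in week 1 as a control (110 > 100). As an intervention site it enrols 88 in week 1 and finishes in week 2.

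The log-SD is ln(71/10) / (2 × 0.6745) = 1.453. The share of hospitals in the four-week level is:
- control: Φ(ln(33.3/29)/1.453) = Φ(0.096) ≈ 54%
- intervention: Φ(ln(41.7/29)/1.453) = Φ(0.249) ≈ 60%.

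**Step 2: approximate size.** Every cut-point rises by a factor 1/f, so hospitals in the middle levels are larger by about log2(1/f) doublings and the false relative risk is about s^log2(1/f).
- f = 0.8: log2(1.25) = 0.322. s = 0.8 gives 0.93, s = 0.9 gives 0.97, s = 1.25 gives 1.07.
- f = 0.9: log2(1/0.9) = 0.152. s = 0.8 gives 0.97.
- f = 0.7: log2(1/0.7) = 0.515. s = 0.8 gives 0.89.
- f = 1 or s = 1: exactly 1.

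**Step 3: simulation of the stopping rule.** Poisson weekly counts, volume capped at 400 a week, ICC 0.015, 300,000 hospitals per arm, no treatment effect:

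| s per doubling | f | Overall RR | Week 1 | Week 2 | Week 3 | Week 4 |
|---|---|---|---|---|---|---|
| 0.8 | 1.0 | 0.998 | 1.002 | 0.983 | 1.005 | 0.996 |
| 0.8 | 0.9 | 0.993 | 0.967 | 0.971 | 0.956 | 0.974 |
| 0.8 | 0.8 | 0.995 | 0.969 | 0.930 | 0.922 | 0.941 |
| 0.9 | 0.8 | 0.999 | 0.981 | 0.965 | 0.959 | 0.975 |
| 1.0 | 0.8 | 1.001 | 1.006 | 0.996 | 0.986 | 1.006 |
| 1.25 | 0.8 | 0.993 | 1.025 | 1.076 | 1.066 | 1.063 |
| 0.8 | 0.6 | 0.979 | 0.919 | 0.852 | 0.845 | 0.875 |

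The rows with f = 1 or s = 1 show simulation noise of up to about 0.02. A second set of runs (400,000 hospitals per scenario, log-normal or gamma volume, s = 0.8 to 0.9) gave 0.97-0.99, 0.93-0.99 and 0.89-0.98 at 10%, 20% and 30% lower capture.

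**Step 4: against sampling error.** With 664 hospitals the null 95% ranges for the stratum relative risk are about 0.70-1.43, 0.67-1.50, 0.61-1.64 and 0.75-1.34 (weeks 1 to 4). For week 4 the standard error is ln(1.34)/1.96 = 0.149. A false ln(0.93) = −0.073 is 0.49 standard errors, so the two-sided 5% error rate becomes Φ(−1.47) + Φ(−2.45) ≈ 8%. Across the four levels the rate is 6-8% at 0.93 and about 8-12% at 0.89.

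**Limit of the model.** The simulated cluster-size CV is 0.80 against the stated 0.63, so the log-normal volume model is only approximate.

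**The case against.** The strongest reply is that the bias needs two conditions together and the documents support neither. Sections 5.2 and 6.1 call for all consecutive adults, 6.2 seeks a waiver of consent to protect consecutive enrolment, and the screening log (7.3 and section 9) allows capture to be compared by arm. The surveillance grid and bedside guide apply only to high-risk patients, and much of that work falls after the patient is already in the trial. No capture loss and no volume-mortality gradient is stated anywhere. Even where both hold, the shift is small beside the sampling error of a single stratum, and a shift common to all levels creates little false heterogeneity, which is what a subgroup analysis looks for. Duration may also be meant to show whether the effect varies with time spent delivering the intervention; the SAP gives no rationale.

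All of this limits the size and likelihood of the problem, and it stands. It does not make duration a baseline variable. Consecutive enrolment is an intention, and keeping a screening log shows that completeness was to be checked.

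A reader might also infer that expected volume is on file for every hospital, so that the replacement needs no new data. The documents do not support that. Sections 5.2 and 7.1 speak of case load or matching on volume, but the operative text in 6.3 and SAP 3.1 does not use it, and 6.5 does not list it.

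**Conclusion.** The point holds in a conditional form. Subgroup ii) is an improper subgroup because its levels are set after allocation at sites that know their arm. That sites know their arm is inferred from 6.4 and the arm-specific forms; the documents do not state it.

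Under no treatment effect, the illustrative false relative risks are about 0.93-0.99 at 20% lower intervention capture with mortality falling 10-20% per doubling of volume. They lie above 1 if mortality rises with volume, and at 1 if capture is equal or volume is unrelated to mortality. These values rest on assumed capture rates and gradients and are not estimates for this trial.

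Three stronger readings should be resisted. The documents do not show that intervention sites enrolled more slowly. They do not fix the direction of any bias. They also do not show that the primary result is compromised: across 10-20% lower capture the simulated overall relative risk stayed at 0.99-1.00, falling to 0.98 only at 40% lower capture with the steep gradient. If missed patients also differed in risk by arm, the primary analysis could be affected, but that is a separate issue and was not examined here.

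**What to change.** In SAP 3.2.2, redefine subgroup ii) by a baseline measure of hospital size. Use the number of operating rooms or beds from the centre form (6.5), in categories fixed without reference to outcomes. Expected weekly surgical volume is preferable if it was recorded before randomisation for every site. Section 6.5 does not say when the centre form is completed, so the SAP should state this, although rooms and beds are unlikely to change with allocation.

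Tabulate duration of recruitment by arm as a process measure, alongside enrolled over eligible patients by arm from the screening log. If effect estimates by duration are kept, label them non-randomised and exploratory.

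The cost is a few lines of SAP text and one extra table. Operating rooms or beds are a cruder proxy for volume than observed throughput, and the replacement does not answer any question about length of time delivering the intervention.
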